AIMS To investigate whether estimated intraperitoneal pressure (eIPP) is correlated to non-infectious PD-related complications in end-stage renal failure patients

OUTCOME MEASURES Measures non-infectious peritoneal complications including hernia, pleuroperitoneal fistulas (PPF), patent processus vaginalis (PPV), retroperitoneal leak and gastrointestinal symptoms since peritoneal dialysis catheter insertion

POPULATION Patients treated with peritoneal dialysis

ELIGIBILITY All adult patients both incident and prevalent to peritoneal dialysis

DURATION Twelve months following study enrolment

REFERENCE DIAGRAM

[figure not shown]

Figure 1 Study Flow Diagram

1. INTRODUCTION

1.1. BACKGROUND

Peritoneal dialysis (PD) is a commonly used renal replacement therapy for patients with end-stage renal disease, which accounts for 9% of renal replacement therapy in the world(1). Significantly lower cost, easy technique to learn at home and less nurse training being required make it a competitive alternative to haemodialysis. Despite the advantages, PD is associated with several complications, including peritonitis, catheter malfunction, and dialysate leaks, which can affect the patient's quality of life and survival(2,3). While studies have shown a relationship between intraperitoneal pressure (IPP) and various abdominal complications(4), invasive measurement of IPP, is logistically difficult, such that the practice of regular IPP measurement and with subsequent titration of dialysate volume is only recommended in children(5,6).

There are studies trying to simplify the measurements by calculating an estimated IPP (eIPP) with simple anthropometry measurements(7–10). Although they show good accuracy in estimating the actual IPP, there is a lack of studies to validate the correlation between eIPP and abdominal complications, including patient reported outcomes. The burden of gastrointestinal symptoms is high in patients treated with PD, the association with IPP is unclear but it is conceivable that high IPP may be associated with bloating and early satiety(11,12).

The aim of this research protocol is to investigate the relationship between eIPP and non-infectious abdominal complications in PD patients.

1.2. RATIONALE FOR CURRENT STUDY

- In peritoneal dialysis patients, there are established methods and equations to measure or estimate IPP(7,9,10,13)
- High IPP is related to reduced ultrafiltration (UF), hernias and peritoneal leak in PD patients(7).
- Current clinical practice does not include IPP measurement in adult patients(14).
- There is a lack of studies to investigate whether eIPP can predict non-infectious abdominal complications in PD patients.

2. STUDY OBJECTIVES

The primary objective of this research protocol is to investigate whether eIPP is correlated to non-infectious PD-related complications in end-stage renal failure patients.

The secondary objective is to assess the relationship of eIPP with patient-reported outcome measures particularly gastrointestinal symptoms.

3. STUDY DESIGN

This will be a basic science study involving procedures with human participants. It is a prospective observational study examining a prospective cohort of patients treated with peritoneal dialysis for kidney failure.

This will include two separate cohorts within the study, an incident cohort which will include all patients from the time of PD catheter insertion until 8 weeks after starting PD. A second prevalent cohort will include all patients treated with PD who are greater than 8 weeks from the start of dialysis. Patients will be recruited to either the incident or prevalent cohort.

A minimum of 150 patients will be recruited to both cohorts, so there will be a total of 300 participants.

The study will involve the delivery of two clinical assessments only, the measurements required to estimate IPP and the administration of the gastrointestinal symptom rating scale (GSRS) questionnaire at three time points. Aside from these additional assessments there will be no changes to clinical care and specifically any changes to intra-peritoneal dialysate volume will only be made by the clinical team caring for the patient without reference to the eIPP or GSRS.

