The estimated IPP will be assessed at Visit 1 using the equations included in Appendix 2 with the Li formula used for the primary outcome measure.

For the prevalent and incident cohorts. Visit 1 will take place at the time of study enrolment. Visit 2 will take place alongside a routine clinic visits between 60 to 120 days after enrolment (2-4 months). Visit 3 will similarly take place between 320 and 380 days (11-13 months) after study enrolment.

Participants who refuse to fill in the GSRS questionnaire or

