3.2. STUDY OUTCOMES

The primary outcome will be the incidence of non-infectious PD-related complications identified by the clinical team caring for the patient including the development of a new:

- Hernia
- Pleuroperitoneal fistula (PPF)
- Patent processus vaginalis (PPV)
- Retroperitoneal leak

The secondary outcome will be:

- changes in patient reported outcome measures on the GSRS at 3 and 12 months following study recruitment.referral for surgical fixation of non-infectious PD-related complications
- modality change to APD
- transfer to haemodialysis due to the non-infectious complications

During the period of 12 months from study enrolment. Radiological imaging is not required for confirmation nor is surgical fixation.

In Visit 2 and 3, participants who 1) refuse to fill in the GSRS questionnaire, 2) loss of adequate mental capacity to fill in the GSRS questionnaire, 3) refuse to consent clinicians to record their: PD modality, prescribed day and night intra-peritoneal volume, adequacy and peritoneal function using peritoneal equilibration test (PET) data, number of peritonitis episodes, hernias, and leakages developed during PD treatment, 4) defaulted follow-up visits, 5) become pregnant, and 6) received renal transplantation, will be recorded as early withdrawal from the study. Their reason to be withdrawal will be recorded. Data before withdrawal will still be used in outcome analysis. Participants who are withdrawing early from the study will receive same standard and schedule of care.

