6. ASSESSMENT AND FOLLOW-UP

All candidates will be followed up for 12 months following initial eIPP measurement. The formal end of this study will be 12 months after the eIPP measurement of the 150th incident cohort patient. No further recruitment to the prevalent cohort group will take place after the recruitment of the 150th incident patient. Incidental findings will not be recorded and reported in this study. Only the outcome mentioned in Section 3.2 will be recorded and analysed. Participants will be advised to report incidental findings to their GP and clinical care team as per local guidelines or standard of care.

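### Incident patients may enter anywhere from catheter insertion to PD week 8 but are all counted for 12 months from enrolment, so the incidence mixes different periods at risk

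*Combined protocol and SAP*

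**What the plan says.** Section 3 (Study Design) takes patients into the incident cohort from insertion of the catheter "until 8 weeks after starting PD". Patients further into PD go to the prevalent cohort.

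Section 3.1 (Study Measures) states that "Visit 1 will take place at the time of study enrolment", and eIPP is estimated at that visit. It asks only those patients already on dialysis to recall earlier symptoms, which implies that others will not have started. At each visit it also records hernias and leakages that arose during PD treatment.

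Section 3.2 (Study Outcomes): "The primary outcome will be the incidence of non-infectious PD-related complications identified by the clinical team", "including the development of a new" hernia, pleuroperitoneal fistula, patent processus vaginalis or retroperitoneal leak. The window is "During the period of 12 months from study enrolment". That phrase is a fragment placed after the secondary outcomes. I read it as covering both lists, because the next sentence is about confirming complications and section 6 agrees: "All candidates will be followed up for 12 months following initial eIPP measurement".

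The Outcome Measures entry of the study summary differs. It ends its list of complications with "gastrointestinal symptoms since peritoneal dialysis catheter insertion", which reads most naturally as a window for the whole list.

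Section 7 specifies descriptive statistics only. Nowhere is PD start made time zero, time at risk defined, or late entry handled.

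**The concern.** The study asks whether estimated pressure is related to mechanical complications of PD, so the relevant exposure is time with dialysate in the abdomen. Under the stated rules, two incident patients with the same 12-month window can have quite different exposure.

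- A patient enrolled at catheter insertion spends the first part of the window without dialysate.
- A patient enrolled at the week-8 limit is observed over PD weeks 8 to 60, and is there only because PD continued that long. A hernia or leak before enrolment is not new, so section 3.2 does not count it.

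The reported incidence would then partly reflect how early sites approach patients, which the protocol leaves open. The incident cohort also carries the power calculation, which allows for no dropout, so there is little slack for lost events.

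**Working it through.** **Inputs from the protocol.** Event rates of 36% (high IPP) and 17% (low IPP), section 7.1. At least 150 incident patients, section 3. Entry limit of 8 weeks after PD start, section 3. Window of 12 months from enrolment, section 3.2.

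**Assumptions, because the documents give no figure.** The 36% and 17% are 52-week risks counted from PD start. Groups are 75 and 75 with a two-sided 5% test. The gap from enrolment to first exchange is 2 to 12 weeks for those enrolled early. The hazard in the first 8 PD weeks is *m* times the later hazard, with *m* from 1 to 5. No pressure-related event occurs before dialysate is used.

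**The plan's own figure.** Section 7.1 gives 146 patients for 36% v 17% at 80% power. The usual two-sided, equal-group calculation gives 84 per group, 168 in all, and 150 patients give 75.6% power. The protocol states neither sidedness nor split. That mismatch is a separate matter; I use 75.6% only as the baseline.

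**Step 1, cumulative hazard over 52 PD weeks.** H = −ln(1 − p). High: −ln(0.64) = 0.446. Low: −ln(0.83) = 0.186.

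**Step 2, enrolment *g* weeks before PD start, constant hazard.** Risk = 1 − exp(−H × (52 − g)/52).
- g = 2: 34.9% v 16.4%, power 74.1%.
- g = 12: 29.1% v 13.4%, power 65.5%.

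**Step 3, enrolment exactly at week 8.** In days, the first PD year carries cumulative hazard proportional to 56m + 309. The window from day 56 to day 421 carries 365. The net loss is 1 − 365/(56m + 309):
- m = 1: 0%.
- m = 2: 56/421 = 13%.
- m = 3: 112/477 = 23%.
- m = 4: 168/533 = 32%.

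**Step 4, what this does to the comparison.** In weeks, the week-8 risk is 1 − exp(−H × 52/(8m + 44)). The last two rows average the risks of three equal groups, enrolled 4 weeks before PD start, at PD start and at week 8.

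| Scenario | High v low | Difference (points) | Ratio | Power, 150 patients |
|---|---|---|---|---|
| All at PD start | 36.0% v 17.0% | 19.0 | 2.1 | 75.6% |
| All 12 weeks before start, m = 1 | 29.1% v 13.4% | 15.7 | 2.2 | 65.5% |
| All at week 8, m = 1 | 36.0% v 17.0% | 19.0 | 2.1 | 75.6% |
| All at week 8, m = 3 | 28.9% v 13.3% | 15.6 | 2.2 | 65.3% |
| All at week 8, m = 5 | 24.1% v 10.9% | 13.2 | 2.2 | 57.0% |
| Mixed thirds, m = 1 | 35.3% v 16.6% | 18.7 | 2.1 | 74.6% |
| Mixed thirds, m = 3 | 33.1% v 15.5% | 17.6 | 2.1 | 71.5% |

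The rows that put the whole cohort at one entry time are extremes. The risk difference and power fall; the risk ratio hardly moves.

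**The case against.** Several counter-arguments have force.

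- *The ratio is not diluted.* A reader might infer that unexposed time and uncounted early events pull the eIPP association toward no effect. On a ratio scale the table shows otherwise: 36/17 = 2.12, and about 2.2 in the extreme scenarios. The documents give no evidence that entry timing is related to eIPP, or that susceptible patients are depleted before entry. This objection stands.
- *The lost share is easily overstated.* A reader might count every event of the first 8 weeks as lost: 56/365 = 15% at constant hazard, and 56m/(56m + 309) = 27%, 35% or 42% for m = 2, 3 or 4. A week-8 entrant's window runs on to week 60, so later events replace some of these. The net figures are those in step 3, and they apply only at the week-8 limit. This stands too.
- *The early peak is assumed.* The documents give no hazard by time on PD and no length for the gap before PD. This stands.
- *Early events are recorded.* Visit 1 captures hernias and leakages on PD, so they are uncounted rather than invisible. This stands for those two; pleuroperitoneal fistula and patent processus vaginalis are not named there.
- *No 12-month proportion is specified.* True: section 7 names no method, so part of the problem follows from that gap. But the window itself is stated, and it starts at enrolment.
- *The summary's window could bring earlier events in.* It contradicts section 3.2 and so leaves the time origin unsettled.

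**Conclusion.** The point holds as one of definition, interpretability and power. The protocol gives conflicting windows, none of which starts at first exchange. Its section 3.2 window mixes time without dialysate with differing stretches of PD, some conditional on still being on PD. The resulting incidence depends on enrolment practice.

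The size rests on assumptions. Entry 12 weeks before PD start would cut the difference from 19.0 to 15.7 points at constant hazard. Entry at week 8 costs nothing at constant hazard, and about 13%, 23% or 32% of cumulative hazard at m = 2, 3 or 4, as a worst case. An even mix of entry times costs about 1 point of power at m = 1 and 4 points at m = 3.

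The documents do not support a claim of bias in the eIPP ratio. That would need entry timing related to eIPP, or susceptible patients having their event or leaving PD before enrolment. Either is possible, and neither could be examined without the dates listed below.

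**What to change.** 1. Reconcile the study summary with section 3.2, so that one window applies to the primary outcome.
2. Record the dates of catheter insertion, first PD exchange, enrolment and each event. PD start is already needed to assign the cohort, and one appendix formula uses months of PD. Section 3.1 does not list event dates, and the analysis cannot be done without them.
3. Analyse the incident cohort on time since first exchange, with each patient entering at the later of enrolment and first exchange.
4. Report how many enrolled before and after PD start. For those not yet on PD, also state which fill volume selects the version of the Li formula, since the protocol does not say.
5. Report separately the hernias and leakages that occurred on PD before enrolment. Delayed entry corrects who is at risk and when, but does not recover those events.

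The cost is a few extra dates and a less simple analysis, with no added visit and no change to care. The 12-month proportion from enrolment can still be shown beside it. The dates are best collected prospectively, so the change should be made before recruitment or early in it.

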3.1. STUDY MEASURES

[figure not shown]
The outline of the study was presented on session 3.

Initial Visit: Enrolment (Visit 1): Baseline demographic data will be recorded at the time of study enrolment including age, sex, chronic kidney disease (CKD) etiology, Charlson comorbidity index, history of polycystic kidney disease, previous abdominal surgery and presence of hernias, catheter technique placement.

The following anthropometric measurements are required:

- 1) Height: measured standing with shoes off
- 2) Weight: measured with shoes off and “empty” of dialysis fluid. If weighed with fluid in PD the fill volume should be subtracted to give a “dry weight”
- 3) The distance from the decubitus plane to mid-axillary line measured using the method described below:
 - a. The decubitus plane is defined as the bed or couch with the patient lying supine (Figure 2 (A))
 - b. The mid-axillary line is found by:
 - i. The patient raises their arm above the head.
 - ii. Locating the apex of the armpit, the deepest part of the armpit that the hand can reach.
 - iii. The midaxillary line is the line parallel to the ground from the apex of the axilla downward along the lateral chest wall. (Figure 2 (B))
 - iv. A level ruler is used to parallel to the ground to align its midline with the midaxillary line located in the previous step.
 - c. Using another level ruler perpendicular to the ground to measure the distance from the midaxillary line to the decubitus plane

- 4) Waist circumference: measured with a tape measure wrapped above the iliac crests around the level of the umbilicus. See Figure 2 (C).

Created in BioRender.com 

Figure 2 Measurements required to estimate IPP: The patient is placed fully supine on a couch (A). The couch defines the decubitus plane, while the mid-axillary line is identified- the distance between these two planes is measured (B). Waist circumference is measured above the iliac crests at the level of the umbilicus (C).

At Visit 1, 2 and 3 the following information will also be recorded: PD modality, prescribed day and night intra-peritoneal volume, adequacy and peritoneal function using peritoneal equilibration test (PET) data, number of peritonitis episodes, hernias, and leakages developed during PD treatment.

The GSRS will be administered at each Visit 1, 2 and 3 using paper questionnaires. At Visit 1 patients who have started dialysis will be asked to recall symptoms in the month prior to starting dialysis.

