4. PARTICIPANT ENTRY

4.1. PRE-REGISTRATION EVALUATIONS

No pre-registration evaluations are required. All patients with kidney failure treated with peritoneal dialysis are eligible.

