7. STATISTICS AND DATA ANALYSIS

7.1. POWER CALCULATION

A small underpowered observational study of measured IPP Castellnaos et al(7), observed an event rate of 36% in a group of patient with high IPP compared with 17% in a group with low IPP. Using these estimates (with alpha of 0.05 with a power of 0.8, including a 0% drop out rate) a minimum of 146 patient will be recruited to the incident cohort. A similar number in the prevalent cohort should confirm any findings.

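### The prevalent cohort pools patients at any time on PD beyond 8 weeks, so high- and low-eIPP patients may be compared at different times on PD, and PD survivors may show a weaker association

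*Combined protocol and SAP*

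**What the plan says.** Section 3 defines two cohorts by time on PD. The first is "an incident cohort which will include all patients from the time of PD catheter insertion until 8 weeks after starting PD". For the other: "A second prevalent cohort will include all patients treated with PD who are greater than 8 weeks from the start of dialysis". Eligibility adds no limit on duration; section 4.1 says "All patients with kidney failure treated with peritoneal dialysis are eligible".

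The exposure, eIPP, is calculated at Visit 1, which is enrolment, and the Li formula serves the primary outcome (section 3.1 and the formula appendix). The outcome is a new hernia, pleuroperitoneal fistula, patent processus vaginalis or retroperitoneal leak. Its window in section 3.2 is "During the period of 12 months from study enrolment", and section 6 agrees: "All candidates will be followed up for 12 months following initial eIPP measurement". The study summary instead describes complications "since peritoneal dialysis catheter insertion".

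The Visit 1 list in section 3.1 begins "Baseline demographic data will be recorded at the time of study enrolment including age, sex, chronic kidney disease (CKD) etiology" and goes on to comorbidity, surgical history and catheter technique. It names neither PD start date nor time on PD. The analysis section commits only to descriptive statistics. Section 7.1 sizes the incident cohort and then says of the other: "A similar number in the prevalent cohort should confirm any findings".

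**The concern.** The 8-week split shows that the design regards early PD as different from later PD. Beyond that point, time on PD plays no part in the comparison. Two separate problems could follow.

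- **Confounding.** If complication risk changes with time on PD, and the eIPP groups differ in their mix of short and long duration, a crude comparison attributes part of the duration effect to eIPP. This could create, inflate or hide an association.
- **Survivor selection.** Prevalent patients are those whose earlier complications did not end PD. If patients differ in susceptibility, the most susceptible high-eIPP patients may already have left, which narrows the contrast among those remaining even when duration is balanced.

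At stake is the confirmatory role that section 7.1 gives this cohort. A weak prevalent result could be read as failing to confirm the incident finding when it only reflects who was still on PD.

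**Working it through.** **Inputs from the documents.** Event rates of 36% (high IPP) and 17% (low IPP), alpha 0.05, power 0.8, no dropout, and 146 patients (section 7.1); 150 per cohort (section 3); the Castellanos coefficient of -0.096 per month of PD (formula appendix). The documents give no risk by time on PD, no distribution of time on PD, and no high/low eIPP cut-off.

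**The plan's own figure.** A two-sided pooled comparison of 36% with 17% in equal groups needs 84 per group, 168 in total, so 146 is not reproduced on those terms. Sidedness and group split are not stated. At 75 per group the two-sided power is 75.6%, which is the baseline used below. The present point does not depend on 146.

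**Link between eIPP and duration.** Li uses waist and the decubitus-to-axillary distance, with constants set by fill volume, and has no duration term. Castellanos gives -0.096 × 24 = -2.3 at 2 years and -0.096 × 60 = -5.8 at 5 years. The documents' only explicit link is therefore in a secondary formula.

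**Illustration 1: confounding, with no true eIPP effect.** Assumed: 12-month risk of 30% early and 15% or 10% late on PD; 60% of the high group and 40% of the low group are early.

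- Late risk 15%: high 0.6 × 30 + 0.4 × 15 = 24%; low 0.4 × 30 + 0.6 × 15 = 21%; ratio 24/21 = 1.14.
- Late risk 10%: high 0.6 × 30 + 0.4 × 10 = 22%; low 0.4 × 30 + 0.6 × 10 = 18%; ratio 22/18 = 1.22.
- Imbalance reversed: 21/24 = 0.88 and 18/22 = 0.82.
- Equal early shares in both groups, or equal early and late risk: ratio 1.00, no bias.

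**Illustration 2: survivor selection.** Assumed: gamma frailty with variance θ; 36% and 17% taken as first-year risks; everyone enters event-free at the same time T (years) on PD. Survival is S(t) = (1 + θLt)^(-1/θ), with L = (S₁^(-θ) - 1)/θ and S₁ = 0.64 or 0.83. The next-year risk is 1 - S(T+1)/S(T). For θ = 1, L = 1/0.64 - 1 = 0.5625 in the high group and 1/0.83 - 1 = 0.2048 in the low group. At T = 3 the high-group risk is 1 - (1 + 0.5625 × 3)/(1 + 0.5625 × 4) = 1 - 2.6875/3.25 = 17.3%.

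| θ | T (years) | High | Low | Power, 75 per group |
|---|---|---|---|---|
| any | 0 | 36% | 17% | 76% |
| 0.5 | 1 | 30.6% | 15.7% | 58% |
| 1 | 1 | 26.5% | 14.5% | 44% |
| 0.5 | 3 | 23.4% | 13.6% | 34% |
| 1 | 3 | 17.3% | 11.3% | 18% |
| none | any | 36% | 17% | 76% |

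If entry is spread uniformly from 8 weeks to 3 years, averaging the risks over entry time gives power of about 51% (θ = 0.5) or 36% (θ = 1).

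**The case against.** The strongest reply is that nothing in the documents shows high- and low-eIPP patients to differ in time on PD. A reader might infer from the Castellanos coefficient that eIPP falls mechanically by 5.8 over five years. That does not carry over to the primary exposure, because Li has no such term. This objection stands: confounding is possible, not demonstrated.

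A reader might also infer that PD start date will not be collected. The documents do not support that. The Visit 1 list is introduced as inclusive rather than exhaustive, cohort assignment needs the date, and Castellanos needs months of PD. What remains is that the item is not listed and the analysis does not use it.

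Nor should the 34-18% be read as the cohort's expected power. It places every patient event-free at 3 years, whereas entry starts at 8 weeks and patients with earlier complications are not excluded. Section 7.1 also attaches no time window to 36% and 17%.

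Finally, no high/low grouping or decision rule is specified outside the power calculation, so misreading a weak result is a risk and not a planned step. That is fair, but the analysis is still open and can be specified now. The summary's window starting at catheter insertion does not help: for prevalent patients it would count events that preceded the eIPP measurement. It should be reconciled with section 3.2.

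**Conclusion.** The point holds in a limited form. The text settles that the prevalent cohort pools all durations beyond 8 weeks, starts the risk window at enrolment and plans no handling of time on PD. High- and low-eIPP patients may therefore be compared at different times on PD.

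The size and direction of any bias are unknown. Confounding vanishes if risk does not change with time on PD or if duration is balanced between eIPP groups. Survivor selection has no effect if patients do not differ in underlying susceptibility. With a modest assumed imbalance, the spurious risk ratio is 1.14 to 1.22, or 0.82 to 0.88 if the imbalance is reversed. The frailty figures show that a real effect could look materially weaker among PD survivors; they do not predict that it will.

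The consequence is confined to the confirmatory cohort, half of the planned 300 participants. The incident cohort, on which the sample size rests, has a narrow entry window and is largely unaffected. The change is worth making because it is cheap and must be specified before the data are seen.

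**What to change.** 1. List PD start date explicitly in the Visit 1 data.
2. For the prevalent cohort, pre-specify that the association between eIPP and complications is adjusted for time on PD at entry. Alternatively, analyse time to first new complication on the time-since-PD-start scale with delayed entry at Visit 1.
3. Show results descriptively by time on PD at entry, for example under 1, 1 to 3 and over 3 years.
4. State that the prevalent estimate applies to patients who have remained on PD, and that it may differ from the incident estimate for that reason alone.
5. Give one risk window in both the summary and section 3.2.

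The cost is one date that is already needed, plus analysis wording. The delayed-entry option also needs the date of each complication, whereas section 3.1 explicitly lists only the number. Estimates by time on PD will be imprecise: three bands by two eIPP groups in 150 patients average 150/6 = 25 per cell. Neither adjustment nor delayed entry removes survivor selection, which is why the interpretation statement is needed as well.
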